The main objective of this clinical trial is to test the efficacy of two different transcranial electrical stimulation techniques (tES) to modify dysfunction of central modulatory mechanisms of pain, and to improve symptoms and quality of life in refractory chronic pain patients.

In this vein, we hypothesize that transcranial electrical stimulation procedures will be more effective than sham to improve pain and related symptoms. Besides, central biomarkers of pain processing and modulation (i.e., CPM, TSSP and EEG) will be useful to predict the patient response to treatment and thus, the efficacy of these tES procedures.

Based in these principal ideas, we propose the following secondary or specific objectives:

- A. To analyse the relationship between the studied biomarkers and clinical pain characteristics of patients (intensity, location, frequency, duration, daily interference caused by pain).
- B. To stratify patients and propose profiles based on the selected biomarkers, which may be useful to improve diagnosis and to guide individualized treatment plans.
- C. To develop home-based treatment schemes for patients with refractory chronic pain. We will assess if tES procedures are safe, feasible and acceptable for the at-home management of this medical condition.
- D. To test if tES techniques are self-manageable by patients and to observe the impact of this treatment in the caregiver-burden declared by the reference person.
- E. To test the efficacy of tDCS (Direct current) versus tACS (Alternant current) to modify dysfunction of central endogenous analgesia (i.e., CPM and TSSP) and to reduce pain and related symptoms in the patients, in a placebo-controlled clinical trial.
- F. To analyze how the different tES techniques (tDCS and tACS) affect brain oscillatory activity, and to test if the changes in oscillatory activity are related to pain relief.
- G. To test the power of the biomarkers/patients' stratification to predict treatment efficacy and to identify the characteristic of best responders patients.

- H. To assess the effect of sex/gender and other modulator variables (age, disease duration, medication, lifestyle, mood...) on all the analyses (central biomarkers, patients' stratification, response to treatment...).

3. Study design

The research is classified as a double-blinded, randomized clinical trial with one control group which receive a sham stimulation.

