Identified caregivers are invited to a brief face-to-face interview to evaluate their burden and health status. Given the exploratory character of this purpose, we do not set a priori sample size for caregivers, although the question about the caregiver will be formulated to all the patients.

5. Description of the treatment

Home-based transcranial electrical stimulation device consists of a custom headgear with fixed electrode sites and built-in cabling made for a simplistic setup for tDCS/tACS stimulation. Systems are equipped with strict dose control feature that provide reliable control over the intensity and timing of stimulation, turning these devices into a feasible and safe clinical alternative.

The equipment is specifically designed for easy and simplistic self-setup and allows the researchers to remotely check the position of electrodes and also monitor the stimulation session. This is possible because the devices have an Internet wireless connection and send the data obtained to an online platform, only accessible to the principal researchers.

From pre-stimulation set-up, to during stimulation monitoring, to post-stimulation confirmation, the device provides an intuitive and clear indication of electrode contact quality, facilitating the proper adjustments to ensure a successful stimulation. In case stimulation is aborted or interrupted, impedance is abnormal, or other faults are detected, the system will automatically abort or alter stimulation and the incident details stored. This system also allows researchers to supervise the treatment compliance.

¹ It must not be overlooked that patients with chronic pain can find difficulties/limitations to accomplish the basic daily tasks and thereby be partially dependant (Meulders, 2019; Zale et al., 2013)

Besides, these devices use a software which allows a double-blinded procedure. Neither the researchers nor the participants will know what kind of stimulation is receiving each of them.

The intervention plan comprises fifteen stimulation sessions applied with a daily frequency during an uninterrupted period of time which covers just over two weeks. Thus, sessions will be scheduled for each patient before the beginning of the treatment, arranging with the patient the hour frame for stimulation. Stimulation parameters/sites for each condition will be as follows:

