The main quantitative statistical analyses to assess the efficacy of transcranial electrical stimulation techniques consist of ANOVA-tests of repeated measures with three groups. Time-measures for each of the above-mentioned endpoints are taken as intragroup variables (pre vs. post), whereas intergroup measures refer to the received stimulation or treatment (tDCS vs. tACS vs. Sham). Thus, both clinical variables (for example, pain intensity, fatigue, sleep quality, disease severity and interference) and potential biomarkers (including brain oscillatory activity registered by EEG, CPM and TSSP response) are considered as intragroup variables.

Those covariates which show a significant correlation with clinical outcomes will be also included in their correspondent ANOVA analysis. These potential covariates are basically age, self-perceived stress, social support, catastrophism and medication intake.

All these statistical analyses will be repeated in separated groups of patients, created in the basis of sex, type and duration of chronic pain, among other characteristics. The objective is to assess whether the clinical outcomes depend on sex or diagnosis, as each tES could be more effective for specific diseases.

CPM/TSSP response and EEG pattern observed before the tES application are also regarded as potential predictors of the treatment efficacy. Thus, the pre-treatment indexes of these biomarkers will be used as independent variables in *Linear regression models*, which includes the clinical improvement in each endpoint as dependent measure. The procedure will be repeated with *Logistic regression analysis* establishing the respondent vs. no-respondent categories as dichotomic variable.

For last, we will register and assess the percentage of dropouts with their respective motives, in order to obtain an index of the feasibility of home-based tES approach. Client

satisfaction index and caregiver interview will also include questions about the capability of participants to manage with tES devices, data which will be qualitatively analysed.

8. Chronogram

WORKING PLAN (WP)		3	6	9	12	15	18	21	24	27	30	33	36
TASK	\ MONTH												
WP1. Development and selection of assessment and monitoring tools for refractory chronic pain patients													
Task 1.1.	Review of the literature and identification of the most common and important variables used as outcomes in clinical trials with chronic pain population.												

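### Feasibility of home treatment is quantified only by the dropout percentage, which does not respond to sessions missed by retained patients; the device data that could show them have no planned analysis

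*Combined protocol and SAP*

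**What the plan says.** Two secondary objectives in section 2 concern home delivery. Objective C reads: "We will assess if tES procedures are safe, feasible and acceptable for the at-home management of this medical condition". Objective D begins: "To test if tES techniques are self-manageable by patients".

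Section 5 sets the planned treatment at "fifteen stimulation sessions applied with a daily frequency during an uninterrupted period of time". It describes devices that connect to the internet and "send the data obtained to an online platform, only accessible to the principal researchers". If a session is interrupted or a fault is detected, "the system will automatically abort or alter stimulation and the incident details stored". It adds: "This system also allows researchers to supervise the treatment compliance".

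The analysis of feasibility is at the end of section 7: "we will register and assess the percentage of dropouts with their respective motives, in order to obtain an index of the feasibility". The next sentence says that the satisfaction index and the caregiver interview will include "questions about the capability of participants to manage with tES devices, data which will be qualitatively analysed".

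Table 1 in section 6.2 lists an ad hoc questionnaire on satisfaction and perceived improvement. It has no endpoint for sessions completed, sessions aborted or adherence. Neither section 6.2 nor section 7 defines dropout.

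**The concern.** Dropout measures retention in the study. Objectives C and D also depend on whether patients, on their own at home, actually deliver the stimulation they were assigned. The two can diverge. A patient may attend every evaluation and answer the daily survey, yet miss a good share of the 15 sessions or have many of them aborted. Nothing in section 7 makes such a patient a dropout, so the index is unchanged.

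A statement that home-based tES is feasible could then rest on retention alone. There is also a lesser consequence for efficacy. Section 7 compares the three arms by repeated-measures ANOVA and lists no exposure measure among its covariates. If the arms do not differ, no prespecified summary would tell the reader how much stimulation was received.

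**Working it through.** **Inputs from the documents.** 120 patients (section 4) and 15 sessions each (section 5). No dropout rate, completion rate or feasibility threshold is stated; section 4 says only that dropout in this population is not negligible. The plan therefore has no figure to reproduce, and the dropout and missed-session values below are assumptions chosen to show how the index behaves.

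**Step 1. Planned sessions.** 120 × 15 = 1,800.

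**Step 2. Share delivered.** Let d be the dropout proportion and m the sessions missed per retained patient. Counting dropouts as zero sessions:

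delivered share = (1 − d) × (15 − m) / 15

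| Dropout index d | Missed per retained patient m | Sessions delivered | Share of 1,800 |
|---|---|---|---|
| 0% | 0 | 1,800 | 100% |
| 0% | 3 | 1,440 | 80% |
| 0% | 5 | 1,200 | 66.7% |
| 0% | 8 | 840 | 46.7% |
| 10% | 0 | 1,620 | 90% |
| 10% | 3 | 1,296 | 72% |
| 10% | 5 | 1,080 | 60% |
| 10% | 8 | 756 | 42% |

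Within each block the index is constant while the delivered share falls by more than half. Counting dropouts as zero is a simplification. At 10% dropout it concerns 12 × 15 = 180 sessions, so crediting sessions done before leaving could add at most 10 percentage points. It has no effect on the 0% rows.

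**Step 3. Precision of the index.** With 120 patients, 0 dropouts has an exact 95% CI of 0% to 3.0%, and 12 dropouts (10%) has 5.3% to 16.8%. A low and fairly precise dropout figure is therefore compatible with any of the delivery levels in its block.

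**Step 4. Whether another planned analysis fills the gap.**

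- Recorded motives for dropout describe only patients who left.
- The satisfaction and caregiver questions address ability to handle the device. They are analysed qualitatively and count no sessions, and caregiver data exist only where a caregiver is identified (section 4).
- Side effects reported in the daily survey (section 6.2) bear on safety.
- The Zarit interview, which section 6.2 says also informs on patient autonomy, measures caregiver burden.
- Compliance supervision (section 5) and daily contact (section 9) are trial conduct, with no outcome or denominator attached.

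None of these reports sessions completed out of 15.

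**The case against.** The strongest reply is that dropout does not stand alone. It is called an index, it comes with motives, and the following sentence adds questions on managing the device, which speak to objective D. Satisfaction is a Table 1 endpoint. This is correct and belongs in any fair description of the plan, but these items are qualitative or concern opinion, so the quantitative gap remains.

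Second, several safeguards make unnoticed skipping less likely: session hours agreed in advance, a training session, video-call help for the first session, compliance supervision and daily contact. This also stands. Completion may turn out to be high, and nothing in the documents favours the assumed 3 or 5 missed sessions over fewer. But if completion is high, the session count is what would demonstrate it.

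Third, section 5 does not say in so many words that the device keeps a record of each completed session. It describes remote monitoring, data upload, stored incidents and supervision of compliance. That a session count can be extracted is a reasonable inference and should be confirmed.

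Fourth, dropout is undefined, so the team might intend to record a patient who stops stimulating as a dropout. The text does not settle this, which is itself a reason to define the term. Even then, a patient who misses only some sessions would still not be captured.

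Finally, the text available shows no work packages 3 and 4 in the chronogram. The absence claimed here is therefore limited to section 7 and Table 1.

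**Conclusion.** As written, the only quantitative index of home-treatment feasibility does not respond to sessions missed by retained patients, and the device data that could reveal them are given no analysis. This affects secondary objectives C and D. It does not change the primary endpoint or its test.

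The size is illustrative only. Under assumed 0% dropout with 3 or 5 of 15 sessions missed per patient, 80% or 67% of sessions are delivered with the index at 0%. The true figures are unknown.

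Three stronger readings are tempting and are not supported:

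- A reader might infer that a patient who stays but skips sessions is counted as a feasibility success, or that 10% dropout would be reported as 90% feasibility. The plan defines no success category and no threshold; such a patient simply is not stated to be a dropout.
- A reader might infer that a complete session log already exists. Section 5 comes close but does not say so.
- A reader might infer that a null efficacy result would be uninterpretable. Because compliance can be supervised, delivery could still be described afterwards; what is missing is prespecification.

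**What to change.** In section 7, and as a line in Table 1:

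1. Make the main quantitative feasibility measure the number of sessions completed out of 15 per randomised patient, taken from the device data and reported by arm with 95% CI. Count sessions not done after dropout as not completed.
2. Define a completed session so that it applies equally to sham, where current flows only during the ramps. State how altered sessions are counted, and whether the training session at the second pre-treatment visit is among the 15.
3. Report the number of aborted or interrupted sessions by arm.
4. Define dropout. Keep its percentage and motives, and the satisfaction and caregiver questions, as supporting descriptors.
5. A pass/fail threshold is optional; if one is used, fix it before unblinding.

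On section 5's description this needs no new procedure and adds no burden for patients. It costs some SAP wording, a check that session counts can be exported, and a little more analysis. The resulting figure may be less favourable than the dropout percentage.
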